6.6. Post-treatment Assessments

6.6.1. Early Study Drugs Discontinuation Assessments

If the subject discontinues study drug prior to the End of Blinded Treatment Visit, the subject will be asked to return to the clinic within 72 hours of stopping study drugs for the Early Study Drugs Discontinuation Visit. The subject will be asked to continue attending the scheduled study visits through the End of Blinded Treatment Visit.

If the subject discontinues study drug during the Open Label rollover extension, the subject will be asked to return to the clinic within 72 hours of stopping the study drug for the Early Study Drugs Discontinuation Visit.

At the Early Study Drugs Discontinuation Visit, any evaluations showing abnormal results indicating that there is a possible or probable causal relationship with the study drug, will be repeated weekly (or as often as deemed prudent by the Investigator) until the abnormality is resolved, returns to Baseline, or is otherwise explained.

The following evaluations are to be completed at the Early Study Drugs Discontinuation Visit:

- Review of AEs and changes in concomitant medications
- Complete physical examination (urogenital/anorectal exams will be performed at the discretion of the Investigator)
- 12-lead ECG performed supine (blinded treatment phase only)
- Vital signs measurement (blood pressure, pulse, respiration rate, and temperature), including weight
- Urine collection for the following laboratory procedures:
 - Urinalysis
 - Urine pregnancy test (females of childbearing potential only); positive urine pregnancy tests will be confirmed with a serum test
- CCU
- Blood sample collection for the following laboratory analyses:
 - Chemistry profile: alkaline phosphatase, AST, ALT, GGT, total bilirubin, direct and indirect bilirubin, total protein, albumin, LDH, CPK, bicarbonate, BUN, calcium, chloride, creatinine, glucose, phosphorus, magnesium, potassium, sodium, uric acid, and amylase (reflex lipase testing is performed in subjects with total amylase > 1.5 × ULN), and TSH

- Estimated glomerular filtration rate according to the Cockcroft-Gault formula
- Hematology profile: complete blood count (CBC) with differential and platelet count
- Plasma HIV-1 RNA
- CD4+ cell count
- Plasma storage sample for safety, virology, or PK testing
- Plasma HBV DNA (for subjects who meet the definition of HBV infection anytime)
- HIV-1 genotype/phenotype testing for subjects with virologic failure
- Drug accountability

6.6.2. 30 Day Follow Up

Subjects who prematurely discontinue study drug during the blinded phase and refuse to continue in the study through the End of Blinded Treatment Visit will be asked to return to the clinic 30 days after the completion of the Early Study Drugs Discontinuation Visit for the 30-Day Follow-Up Visit.

Those subjects who prematurely discontinue study drug during the blinded phase and continue in the study through at least one subsequent visit after the Early Study Drug Discontinuation Visit will not be required to complete the 30-Day Follow-Up Visit.

Subjects who complete the study drugs through the End of Blinded Treatment Visit and who do not participate in the open-label rollover extension, will be required to return to the clinic 30 days after the completion of study drug for the 30 Day Follow Up visit.

Subjects who prematurely discontinue study drug during the Open Label rollover extension will be asked to return to the clinic 30 days after the completion of the Early Study Drugs Discontinuation Visit for the 30-day Follow-Up Visit. The subject will not continue attending the scheduled study visits.

Subjects who complete the Open Label rollover extension will be asked to return to the clinic 30 days after the completion of the study drugs for the 30-day Follow-Up Visit.

For the purpose of scheduling a 30-Day Follow-Up Visit, a ± 6 days window may be used. The following evaluations are to be completed at the 30-Day Follow-Up Visit:

- Review of AEs and changes in concomitant medications
- Symptom-directed physical examination

- Vital signs measurement (blood pressure, pulse, respiration rate, and temperature), including weight
- Urine collection for the following laboratory procedures:
 - Urinalysis
 - Urine pregnancy test (females of childbearing potential only); positive urine pregnancy tests will be confirmed with a serum test.
- Blood sample collection for the following laboratory analyses:
 - Chemistry profile: alkaline phosphatase, AST, ALT, GGT, total bilirubin, direct and indirect bilirubin, total protein, albumin, LDH, CPK, bicarbonate, BUN, calcium, chloride, creatinine, glucose, phosphorus, magnesium, potassium, sodium, uric acid, and amylase (reflex lipase testing is performed in subjects with total amylase $> 1.5 \times \text{ULN}$).
 - Estimated glomerular filtration rate according to the Cockcroft-Gault formula
 - Hematology profile: complete blood count (CBC) with differential and platelet count
 - Plasma HIV-1 RNA
 - CD4+ cell count

At the 30-Day Follow-Up Visit, any evaluations showing abnormal results believed to be a reasonable possibility of a causal relationship with the study drugs will be repeated weekly (or as often as deemed prudent by the Investigator) until the abnormality is resolved, returns to baseline, or is otherwise explained.

6.7. Criteria for Discontinuation of Study Treatment

Study medication will be discontinued in the following instances:

- Unacceptable toxicity, or toxicity that, in the judgment of the investigator, compromises the ability to continue study-specific procedures or is considered to not be in the subject's best interest
- Subject request to discontinue for any reason
- Pregnancy during the study; refer to [Appendix 7](#)
- Development of active tuberculosis infection

Study medication may be discontinued in the following instances:

- Intercurrent illness that would, in the judgment of the investigator, affect assessments of clinical status to a significant degree. Following resolution of intercurrent illness, the subject may resume study dosing at the discretion of the investigator
- Lack of efficacy
- Subject noncompliance
- Discontinuation of the study at the request of Gilead, a regulatory agency or an institutional review board or independent ethics committee (IRB/IEC)

6.8. Blood and Urine Storage

CCI

6.9. Assessments for Premature Discontinuation from Study

If a subject discontinues study dosing (for example, as a result of an AE), every attempt should be made to keep the subject in the study and continue to perform the required study-related follow-up and procedures (see Section 6.7, Criteria for Discontinuation of Study Treatment). If this is not possible or acceptable to the subject or investigator, the subject may be withdrawn from the study.

6.10. End of Study

The end of study will be the last patient's last observation (or visit).

6.11. Post Study Care

After a subject has completed/terminated their participation in the study, long-term care for the subject will remain the responsibility of their primary treating physician.

6.12. Virologic Failure

Virologic failure is defined as virologic rebound or having HIV-1 RNA \geq 50 copies/mL at study drug discontinuation, Week 48, Week 96, Week 144, Week 48 OL or Week 96 OL.

6.12.1. Management of Virologic Rebound

Subjects who meet the criteria listed below will be considered to have virologic rebound:

- At any visit, after achieving HIV-1 RNA < 50 copies/mL, a rebound in HIV-1 RNA \geq 50 copies/mL, which is subsequently confirmed at the following scheduled or unscheduled visit; OR
- At any visit, a > 1 log₁₀ increase in HIV-1 RNA from the nadir which is subsequently confirmed at the following scheduled or unscheduled visit

Following the unconfirmed virologic rebound, subjects will be asked to return to the clinic for a scheduled or unscheduled blood draw (2 to 3 weeks after the date of the original test that resulted in HIV-1 RNA virologic rebound) for confirmation of virologic rebound. If virologic rebound is confirmed at the scheduled or unscheduled visit and the HIV-1 RNA is \geq 200 copies/mL, the blood sample from the confirmation visit will be the primary sample used for HIV-1 genotypic and phenotypic testing. Subjects with documented non-adherence within 72 hours of the visit may not be tested for resistance. After a subject's first post-baseline resistance test, additional testing will be conducted on a case-by-case basis. Any subject may be discontinued at Investigator's discretion or per local treatment guidelines.

[figure not shown]
If no resistance is detected from the genotype or phenotype, the subject may remain on study drugs and a repeat HIV-1 RNA should be repeated (2 to 3 weeks after date of test with HIV-1 RNA \geq 50 copies/mL). Investigators should carefully evaluate the benefits and risks of remaining on study drug for each individual subject and document this assessment in the on-site medical record.

Subjects who are noncompliant on an ongoing basis will be considered for discontinuation per the Investigator's discretion or local treatment guidelines. Investigators who opt to discontinue study drugs for an individual subject must discuss with the Medical Monitor prior to study drug discontinuation.

For subjects who are off study drug but remain on study, it will be the Investigator's discretion to manage virologic rebound.

Please refer to [Figure 6-1](#) for the management of subjects who meet the criteria for virologic rebound.

Figure 6-1. Virologic Rebound Schema

- a If virologic rebound is not confirmed, the subject will remain on their current regimen.
- b If virologic rebound is confirmed and the HIV-1 RNA is ≥ 200 copies/mL, the HIV-1 genotype and phenotype (reverse transcriptase, protease and integrase) will be analyzed.
- c Based on the results of the genotypic and phenotypic assays, the subject will remain on study drugs or study drugs will be discontinued. If genotyping or phenotyping assay fails, a new ARV regimen may be configured at the discretion of the Investigator.
- d If no resistance is detected, HIV-1 RNA will be repeated (2-3 weeks later). Investigator reviews study drug continuation/discontinuation options and discusses with the Medical Monitor prior to study drug discontinuation
- e A new ARV regimen will be configured, at the Investigator's discretion, and the subject will remain in the study.

6.12.2. Subjects with HIV-1 RNA ≥ 50 copies/mL at Study Discontinuation, Week 48, 96, 144, Week 48 OL or Week 96 OL

Subjects with HIV-1 RNA ≥ 50 copies/mL at study discontinuation or last visit will be considered virologic failures. Subjects with HIV-1 RNA ≥ 50 copies/mL at Week 48, Week 96, Week 144, Week 48 OL or Week 96 OL will be asked to return for an unscheduled visit within the visit window for a retest.

Subjects with HIV-1 RNA ≥ 200 copies/mL at study drug discontinuation, last visit, Week 48, Week 96, Week 144, Week 48 OL or Week 96 OL will also have resistance testing conducted.

7. ADVERSE EVENTS AND TOXICITY MANAGEMENT

7.1. Definitions of Adverse Events, Adverse Reactions, and Serious Adverse Events

7.1.1. Adverse Events

An adverse event (AE) is any untoward medical occurrence in a clinical study subject administered a medicinal product, which does not necessarily have a causal relationship with the treatment. An AE can therefore be any unfavorable and/or unintended sign, symptom, or disease temporally associated with the use of a medicinal product, whether or not considered related to the medicinal product. AEs may also include pre- or post-treatment complications that occur as a result of protocol specified procedures, lack of efficacy, overdose, drug abuse/misuse reports, or occupational exposure. Preexisting events that increase in severity or change in nature during or as a consequence of participation in the clinical study will also be considered AEs.

An AE does not include the following:

- Medical or surgical procedures such as surgery, endoscopy, tooth extraction, and transfusion. The condition that led to the procedure may be an adverse event and must be reported.
- Pre-existing diseases, conditions, or laboratory abnormalities present or detected before the screening visit that do not worsen
- Situations where an untoward medical occurrence has not occurred (e.g., hospitalization for elective surgery, social and/or convenience admissions)
- Overdose without clinical sequelae (see Section 7.6.1)
- Any medical condition or clinically significant laboratory abnormality with an onset date before the consent form is signed and not related to a protocol-associated procedure is not an AE. It is considered to be pre-existing and should be documented on the medical history eCRF.

7.1.2. Serious Adverse Events

A **serious adverse event** (SAE) is defined as an event that, at any dose, results in the following:

- Death
- Life-threatening (Note: The term “life-threatening” in the definition of “serious” refers to an event in which the subject was at risk of death at the time of the event; it does not refer to an event that hypothetically might have caused death if it were more severe.)
- In-patient hospitalization or prolongation of existing hospitalization

- Persistent or significant disability/incapacity
- A congenital anomaly/birth defect
- A medically important event or reaction: such events may not be immediately life-threatening or result in death or hospitalization but may jeopardize the subject or may require intervention to prevent one of the other outcomes constituting SAEs. Medical and scientific judgment must be exercised to determine whether such an event is reportable under expedited reporting rules. Examples of medically important events include intensive treatment in an emergency room or at home for allergic bronchospasm; blood dyscrasias or convulsions that do not result in hospitalization; and development of drug dependency or drug abuse. For the avoidance of doubt, infections resulting from contaminated medicinal product will be considered a medically important event and subject to expedited reporting requirements.

7.1.3. Clinical Laboratory Abnormalities and Other Abnormal Assessments as Adverse Events or Serious Adverse Events

Laboratory abnormalities without clinical significance are not recorded as AEs or SAEs. However, laboratory abnormalities (eg, clinical chemistry, hematology, and urinalysis) that require medical or surgical intervention or lead to IMP interruption, modification, or discontinuation must be recorded as an AE, as well as an SAE, if applicable. In addition, laboratory or other abnormal assessments (eg, electrocardiogram, x-rays, vital signs) that are associated with signs and/or symptoms must be recorded as an AE or SAE if they meet the definition of an AE or SAE as described in Sections 7.1.1 and 7.1.2. If the laboratory abnormality is part of a syndrome, record the syndrome or diagnosis (eg, anemia), not the laboratory result (ie, decreased hemoglobin).

For specific information on handling of clinical laboratory abnormalities in this study, please refer to Section 7.5.

7.2. Assessment of Adverse Events and Serious Adverse Events

The investigator or qualified subinvestigator is responsible for assessing AEs and SAEs for causality and severity, and for final review and confirmation of accuracy of event information and assessments.

7.2.1. Assessment of Causality for Study Drugs and Procedures

The investigator or qualified subinvestigator is responsible for assessing the relationship to IMP therapy using clinical judgment and the following considerations:

- **No:** Evidence exists that the adverse event has an etiology other than the IMP. For SAEs, an alternative causality must be provided (eg, pre-existing condition, underlying disease, intercurrent illness, or concomitant medication).
- **Yes:** There is reasonable possibility that the event may have been caused by the investigational medicinal product.

It should be emphasized that ineffective treatment should not be considered as causally related in the context of adverse event reporting.

The relationship to study procedures (eg, invasive procedures such as venipuncture or biopsy) should be assessed using the following considerations:

- **No: Evidence** exists that the adverse event has an etiology other than the study procedure.
- **Yes:** The adverse event occurred as a result of protocol procedures, (eg, venipuncture)

7.2.2. Assessment of Severity

AE severity should be recorded and graded according to the GSI Grading Scale for Severity of Adverse Events and Laboratory Abnormalities ([Appendix 5](#)). For adverse events associated with laboratory abnormalities, the event should be graded on the basis of the clinical severity in the context of the underlying conditions; this may or may not be in agreement with the grading of the laboratory abnormality.

The distinction between the seriousness and the severity of an adverse event should be noted. Severe is a measure of intensity; thus, a severe reaction is not necessarily a serious reaction. For example, a headache may be severe in intensity, but would not be classified as serious unless it met one of the criteria for serious events.

For AEs associated with laboratory abnormalities, the event should be graded on the basis of the clinical severity in the context of the underlying conditions; this may or may not be in agreement with the grading of the laboratory abnormality.

7.3. Investigator Requirements and Instructions for Reporting Adverse Events and Serious Adverse Events to Gilead

Requirements for collection prior to study drug initiation:

After informed consent, but prior to initiation of study medication, the following types of events should be reported on the eCRF:

- all SAEs and adverse events related to protocol-mandated procedures.

7.3.1. Adverse Events

Following initiation of study medication, collect all AEs, regardless of cause or relationship, until 30-days after last administration of study IMP must be reported to the eCRF database as instructed.

All AEs should be followed up until resolution or until the adverse event is stable, if possible. Gilead Sciences may request that certain AEs be followed beyond the protocol defined follow up period.

7.3.2. Serious Adverse Events

All SAEs, regardless of cause or relationship, that occurs after the subject first consents to participate in the study (i.e, signing the informed consent) and throughout the duration of the study, including the protocol-required post treatment follow-up period, must be reported to the eCRF database and Gilead Pharmacovigilance and Epidemiology (PVE) as instructed. This also includes any SAEs resulting from protocol-associated procedures performed after informed consent is signed.

Any SAEs and deaths that occur after the post treatment follow-up visit but within 30-days or 4 weeks of the last dose of study IMP, regardless of causality, should also be reported.

Investigators are not obligated to actively seek SAEs after the protocol defined follow up period; however, if the investigator learns of any SAEs that occur after study participation has concluded and the event is deemed relevant to the use of IMP, he/she should promptly document and report the event to Gilead PVE.

Electronic Serious Adverse Event (eSAE) Reporting Process

- Site personnel record all SAE data in the eCRF database and from there transmit the SAE information to Gilead PVE within 24 hours of the investigator's knowledge of the event. Detailed instructions can be found in the eCRF completion guidelines.
- If it is not possible to record and submit the SAE information electronically, because the eCRF database cannot be accessed or is not available (including at study start), record the SAE on the paper serious adverse event report form and submit by fax or email within 24 hours of the investigator's knowledge of the event to:

Gilead PVE contact information: Email: PPD [REDACTED]
Fax: PPD [REDACTED]

- As soon as it is possible to do so, any SAE reported via paper must be transcribed into the eCRF Database according to instructions in the eCRF completion guidelines.
- If an SAE has been reported via a paper form because the eCRF database has been locked, no further action is necessary.
- All AEs and SAEs will be recorded in the eCRF database within the timelines outlined in the eCRF completion guideline.
- For fatal or life-threatening events, copies of hospital case reports, autopsy reports, and other documents are also to be submitted by e-mail or fax only when requested and applicable. Transmission of such documents should occur without personal subject identification, maintaining the traceability of a document to the subject identifiers.

- Additional information may be requested to ensure the timely completion of accurate safety reports.
- Any medications necessary for treatment of the SAE must be recorded onto the concomitant medication section of the subject's eCRF and the event description section of the SAE form.

7.4. Gilead Reporting Requirements

Depending on relevant local legislation or regulations, including the applicable US FDA Code of Federal Regulations, the EU Clinical Trials Directive (2001/20/EC) and relevant updates, and other country-specific legislation or regulations, Gilead may be required to expedite to worldwide regulatory agencies reports of SAEs, serious adverse drug reactions (SADRs), or suspected unexpected serious adverse reactions (SUSARs). In accordance with the EU Clinical Trials Directive (2001/20/EC), Gilead or a specified designee will notify worldwide regulatory agencies and the relevant IEC in concerned Member States of applicable SUSARs as outlined in current regulations.

Assessment of expectedness for SAEs will be determined by Gilead using reference safety information specified in the investigator's brochure, EU Summary of Product Characteristics (SmPC), or relevant local label as applicable.

All investigators will receive a safety letter notifying them of relevant SUSAR reports associated with any study IMP. The investigator should notify the IRB or IEC of SUSAR reports as soon as is practical, where this is required by local regulatory agencies, and in accordance with the local institutional policy.

7.5. Toxicity Management

All clinical and clinically significant laboratory toxicities will be managed according to uniform guidelines detailed in [Appendix 4](#) as outlined below.

- Clinical events and clinically significant laboratory abnormalities will be graded according to the GSI Grading Scale for Severity of Adverse Events and Laboratory Abnormalities ([Appendix 5](#)).
- Grade 3 and 4 clinically significant laboratory abnormalities should be confirmed by repeat testing within 3 calendar days of receipt of results and before investigational medicinal product discontinuation, unless such a delay is not consistent with good medical practice

Any questions regarding toxicity management should be directed to the Gilead Medical Monitor.

7.5.1. Grades 1 and 2 Laboratory Abnormality or Clinical Event

Continue study drug at the discretion of the Investigator.

7.5.2. Grade 3 Laboratory Abnormality or Clinical Event

- For Grade 3 clinically significant laboratory abnormality or clinical event, investigational medicinal product may be continued if the event is considered to be unrelated to investigational medicinal product.
- For a Grade 3 clinical event, or clinically significant laboratory abnormality confirmed by repeat testing, that is considered to be related to investigational medicinal product, investigational medicinal product will be withheld until the toxicity returns to Grade 2. When restarting investigational medicinal product following resolution of the adverse event, the investigational medicinal product should be restarted at full dose upon discussion with the Gilead Sciences Medical Monitor.
- If a laboratory abnormality recurs to \geq Grade 3 following rechallenge with investigational medicinal product and is considered related to investigational medicinal product, then investigational medicinal product will be permanently discontinued and the subject managed according to local practice. Recurrence of laboratory abnormalities considered unrelated to investigational medicinal product may not require permanent discontinuation but requires discussion with the Gilead Sciences Medical Monitor.

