1.8. Risk/Benefit Assessment for the Study

All patients with HIV-1 infection should receive effective antiretroviral therapy. Potential risks associated with all classes of ARVs include immune reconstitution syndrome, lipodystrophy, and lactic acidosis with steatosis. The risk of class effects is considered to be low. Important identified risks appropriately managed by study inclusion/exclusion criteria as well as through close clinical and laboratory monitoring during the study, are as follows: hypersensitivity reaction to dolutegravir, including liver injury, and allergy to any components of the tablets. Interim data will also be reviewed by an independent data monitoring committee. Potential benefits may include provision of a new antiretroviral therapy that is not currently available and which may have fewer side effects than alternative therapies. Other potential benefits include provisions of fixed dose combination therapy, and the knowledge that patient participation will contribute to the body of knowledge of HIV therapies.

Following a chronic 39 week study in monkeys, animals administered the highest dose of GS-9883 (1000 mg/kg/day) had bile duct hyperplasia (increased cell growth) and hypertrophy (increased cell size), and some increased cell growth and inflammation in nearby liver cells. These effects were not seen in monkeys administered the mid-level dose (200 mg/kg/day), and these animals had plasma GS-9883 exposures that were approximately 5-fold above human exposures when given the GS-9883/F/TAF FDC. No adverse drug reactions associated with liver or bile duct problems have been identified in humans treated with GS-9883. Potential hepatobiliary toxicity is appropriately managed by study inclusion/exclusion criteria, close clinical and laboratory monitoring, as well as specific toxicity management guidance to investigators (Refer to Section 7.5.5.).

Potential benefits of GS-9883 may include provision of a new antiretroviral therapy that is not currently available and which may have fewer side effects than alternative therapies. Other potential benefits include provisions of fixed dose combination therapy, and the knowledge that patient participation will contribute to the body of knowledge of HIV therapies.

The overall benefit-risk assessment for GS-9883/F/TAF and DTG + F/TAF is favorable at this time.

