7.5.3. Grade 4 Laboratory Abnormality or Clinical Event

- For a Grade 4 clinical event or clinically significant Grade 4 laboratory abnormality confirmed by repeat testing that is considered related to investigational medicinal product, investigational medicinal product will be permanently discontinued and the subject managed according to local practice. The subject should be followed as clinically indicated until the laboratory abnormality returns to baseline or is otherwise explained, whichever occurs first. A clinically significant Grade 4 laboratory abnormality that is not confirmed by repeat testing should be managed according to the algorithm for the new toxicity grade.
- Investigational medicinal product may be continued without dose interruption for a clinically non-significant Grade 4 laboratory abnormality (eg, Grade 4 CK after strenuous exercise, or triglyceride elevation that is nonfasting or that can be medically managed) or a clinical event considered unrelated to investigational medicinal product requires discussion with the Gilead Sciences Medical Monitor.

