Arthritis See also Arthralgia	Stiffness or joint swelling causing no or minimal interference with usual social & functional activities	Stiffness or joint swelling causing greater than minimal interference with usual social & functional activities	Stiffness or joint swelling causing inability to perform usual social & functional activities	Disabling joint stiffness or swelling causing inability to perform basic self-care functions
Bone Mineral Loss Pediatric < 21 Years	BMD t-score or z-score -2.5 to -1.0 BMD z-score -2.5 to -1.0	BMD t-score or z-score < -2.5 BMD z-score < -2.5	Pathological fracture (including loss of vertebral height) Pathological fracture (including loss of vertebral height)	Pathologic fracture causing life-threatening consequences Pathologic fracture causing life-threatening consequences
Myalgia (non-injection site)	Muscle pain causing no or minimal interference with usual social & functional activities	Muscle pain causing greater than minimal interference with usual social & functional activities	Muscle pain causing inability to perform usual social & functional activities	Disabling muscle pain causing inability to perform basic self-care functions
Osteonecrosis	NA	Asymptomatic with radiographic findings AND No operative intervention indicated	Symptomatic bone pain with radiographic findings OR Operative intervention indicated	Disabling bone pain with radiographic findings causing inability to perform basic self-care functions

SYSTEMIC				
	Grade 1	Grade 2	Grade 3	Grade 4
Acute Systemic Allergic Reaction	Localized urticaria (wheals) with no medical intervention indicated	Localized urticaria with medical intervention indicated OR Mild angioedema with no medical intervention indicated	Generalized urticaria OR Angioedema with medical intervention indicated OR Symptomatic mild bronchospasm	Acute anaphylaxis OR Life-threatening bronchospasm OR laryngeal edema
Chills	Symptoms causing no or minimal interference with usual social & functional activities	Symptoms causing greater than minimal interference with usual social & functional activities	Symptoms causing inability to perform usual social & functional activities	NA

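### Section 7.5.2 permits a full-dose restart after a related Grade 3 allergic reaction, and its stop-on-recurrence bullet names only laboratory abnormalities

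*Protocol*

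**What the plan says.** Section 7.5.2 of the protocol is headed for both laboratory abnormalities and clinical events. Its first bullet lets study drug continue if the Grade 3 event is unrelated. Its second bullet covers a Grade 3 clinical event, or a confirmed and clinically significant laboratory abnormality, "that is considered to be related to investigational medicinal product, investigational medicinal product will be withheld until the toxicity returns to Grade 2". The restart sentence follows: "When restarting investigational medicinal product following resolution of the adverse event, the investigational medicinal product should be restarted at full dose upon discussion with" the Medical Monitor. The third bullet is the only one on recurrence. It opens "If a laboratory abnormality recurs to" Grade 3 or higher and continues "following rechallenge with investigational medicinal product and is considered related to investigational medicinal product, then investigational medicinal product will be permanently discontinued".

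Four other places bear on the point:

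- Section 7.5.3 requires a permanent stop for related Grade 4 events and names both types: "For a Grade 4 clinical event or clinically significant Grade 4 laboratory abnormality confirmed by repeat testing".
- Appendix 5 defines a Grade 3 acute systemic allergic reaction as "Generalized urticaria OR Angioedema with medical intervention indicated OR Symptomatic mild bronchospasm".
- Section 1.8 lists among the important identified risks "hypersensitivity reaction to dolutegravir, including liver injury, and allergy to any components of the tablets".
- Section 6.7 requires a stop for unacceptable toxicity, or for toxicity that in the investigator's judgment "compromises the ability to continue study-specific procedures or is considered to not be in the" subject's best interest. It also requires a stop at the subject's request.

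Section 7.5 refers to Appendix 4 for the detailed guideline. Only the title of Appendix 4 is readable in the text available here.

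**The concern.** An allergic reaction attributed to study drug is the kind of event for which re-exposure is usually barred outright rather than decided case by case. Section 7.5.2 sets out a hold, a restart threshold and a restart dose that apply to such a reaction without exception. This is therefore a stated rule that covers the case, not silence on it. Exclusion criterion 9 in Section 4.3 screens out only known excipient allergies, so it cannot catch a first reaction on study.

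The recurrence bullet raises a lesser question. A related laboratory value that returns to Grade 3 after rechallenge is a mandatory stop. A related clinical event that returns at the same grade is not, and no reason is given for the difference. What is at stake is the safety of a small number of subjects, not the efficacy result.

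**Working it through.** There is no figure in the plan to reproduce. The check is a reading of the text, followed by two short calculations for scale.

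**Step 1. A related Grade 3 allergic reaction under Section 7.5.2.** Generalized urticaria, treated angioedema or symptomatic mild bronchospasm is a Grade 3 clinical event in Appendix 5, so the second bullet applies. Study drug is withheld until Grade 2. On the same Appendix 5 row, Grade 2 still includes localized urticaria needing intervention and mild angioedema. The restart sentence then speaks of resolution rather than Grade 2, so the restart point is not fully clear. Restart is at full dose after discussion with the Medical Monitor. No event type is excepted.

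**Step 2. The two event types side by side (related events).**

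| Stage | Laboratory abnormality | Clinical event |
|---|---|---|
| Condition for a Grade 3 hold | Clinically significant and confirmed by repeat test | None beyond relatedness |
| Length of hold | Until Grade 2 | Until Grade 2 |
| Restart | Full dose, Medical Monitor discussion | Same |
| Recurs at Grade 3 after rechallenge | Permanent stop | No recurrence rule; hold applies again, then judgment |
| Recurs at Grade 4 | Permanent stop | Permanent stop (Section 7.5.3) |

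The clinical rule is less strict in one row only, recurrence at Grade 3. At the hold step it is the stricter of the two.

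**Step 3. How many subjects.** Section 1.2.3.3 reports 98 treated Phase 2 subjects and no related Grade 3 or 4 adverse event through Week 24. With 0 of 98, the one-sided 95% exact upper bound u solves (1 − u)^98 = 0.05:

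u = 1 − 0.05^(1/98) = 0.030, or 3.0%; 600 × u ≈ 18 subjects.

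This is a ceiling for all related Grade 3 or 4 events over 24 weeks. It includes Grade 4 events that Section 7.5.3 already covers. Allergic reactions and recurrences are a subset whose size the documents do not give.

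**Step 4. What an extra permanent stop costs.** Under the snapshot algorithm (Section 8.5.1.2), a subject who stops for an adverse event with no on-treatment HIV-1 RNA in the Week 48 window does not count as a responder. With 300 per group, one such subject lowers that group's response rate by at most 1/300 = 0.33 percentage points, against a margin of 12 points.

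**The case against.** The strongest objection is that Section 7.5.2 is an outline and Appendix 4 holds the detail. Appendix 4 cannot be read here, and text lost in extraction is not missing from the plan. This stands. The finding concerns the wording of Section 7.5.2 and cannot be extended to the whole protocol. If Appendix 4 already contains either step, what remains is to bring the two texts into line.

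The second objection is that readable text already gives control. A repeat Grade 3 event is held again, restart goes through the Medical Monitor, Section 6.7 requires a stop for unacceptable toxicity, and Section 7.5.3 stops related Grade 4 events, which include anaphylaxis. This also largely stands. A reader might infer that the protocol compels re-exposure or has no safeguard. It does neither: the restart sentence is conditional. But the Section 6.7 stop rests on judgment and mentions neither allergy nor rechallenge, so it does not replace a fixed bar.

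Third, a mandatory stop for every recurrent related Grade 3 clinical event would also take in headache, nausea, insomnia and fatigue, and relatedness needs only a reasonable possibility (Section 7.2.1). Case-by-case handling of these is a defensible choice. This stands, and it makes the recurrence change optional.

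A reader might also argue that blinding makes matters worse, because the investigator restarts without knowing whether the subject took dolutegravir. The documents give this little weight. Section 1.8 names allergy to any tablet component as well, so knowing the assignment would not clear a rechallenge. Under Section 5.1.1, disclosing the assignment to the investigator ends study treatment anyway. In the open-label extension no subject receives dolutegravir.

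**Conclusion.** The point holds within limits. As written, Section 7.5.2 permits a full-dose restart after a related Grade 3 acute systemic allergic reaction, subject only to Medical Monitor discussion and the judgment-based stop in Section 6.7. That should be changed, because the protocol itself names hypersensitivity as an important identified risk. The laboratory-only recurrence bullet is a smaller inconsistency that can be settled either way, provided the choice is written down.

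Two broader inferences are not supported. Section 7.5.2 is not weaker for clinical events in general; it is less prescriptive only when a Grade 3 event recurs. And the 3.0% bound is not an estimate of allergic reactions or of recurrences.

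The number of subjects affected is probably small and cannot be estimated from the documents. The conclusion assumes that Appendix 4 does not already contain the exception. The primary conclusion is not affected: the possible cost is at most 0.33 points per extra stop, and SAP Section 2.2.1 records the Week 48 analysis as already done.

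**What to change.** **Main change.** Add to the restart bullet of Section 7.5.2:

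> Investigational medicinal product will not be restarted after a Grade 3 Acute Systemic Allergic Reaction (Appendix 5) considered related to investigational medicinal product.

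**Optional change.** Either extend the recurrence bullet to *a laboratory abnormality or clinical event*, or state that recurrent related Grade 3 clinical events are handled case by case with the Medical Monitor.

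Check both against Appendix 4 first and align the two texts.

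The cost is one or two sentences, with no added visits or tests. A few subjects who might have tolerated rechallenge would stop study drug. In the blinded phase they can stay in follow-up (Section 6.9), although they may count as non-responders in the snapshot. In the open-label extension they would leave scheduled visits after stopping (Section 6.6.2).
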